4.4 Exclusion Criteria

Subjects will not be enrolled if they meet any of the following:

1. Prior surgical treatment of the nasal valve
2. Rhinoplasty, septoplasty, inferior turbinate reduction or other surgical nasal procedures within the past three (3) months
3. Severe and/or chronic sinusitis, recurrent sinusitis, or allergies leading to nasal obstruction and currently requiring oral corticosteroid therapy
4. Severe case of any of the following: septal deviation, turbinate hypertrophy, polyps, or ptotic nose tip believed to be the primary contributor to the subject's nasal obstruction symptoms and warranting surgical intervention
5. Known or suspected allergies or contraindications to the anesthetic agents and/or antibiotic medications to be used during the study procedure session
6. Known or suspected to be pregnant, or is lactating
7. Other medical conditions which in the opinion of the investigator could predispose the subject to poor wound healing or increased surgical risk.

4.5 Subject recruitment

Patients will be primarily recruited from the clinical population being seen by physicians as part of their practice in the Department of Otolaryngology, The Ohio State University School of Medicine. In order to ensure the subject population has adequate access to the recruitment materials, IRB approved flyers will be available in the patient waiting area, and on the department's website / Facebook page.

4.6 Measurement / Instrumentation

Endoscopic Examination

Patients will receive endoscopic examination as part of their standard clinical care. The severity of disease will be scored based on endoscopic examination (Lund-Kennedy endoscopic scores).

Study Procedures

Each visit is expected to last 2-3 hours and may include the following procedures. (These procedures are routinely performed for research purposes; however, none of them should be considered standard clinical care. The differences will be explained to the participants during the consent process.)

1. All participants will be asked to fill out a medical history questionnaire, as well as the Sino-Nasal Outcome Test (SNOT-22) questionnaire, the NOSE score and the Visual Analog Scale for nasal obstruction. The SNOT-22 and NOSE are two commonly used validated outcome questionnaires to evaluate change in rhinosinusitis and/or nasal obstruction symptoms in patients. The VAS is a self-rating of nasal obstruction on a linear scale (range 0-10; 0 being completely clear and 10 being completely blocked) using both nostrils and then with the left and right nostril separately.
2. Peak nasal inspiratory flow: A mask attached to a spirometer is fitted tightly on each subject's face without touching the nose. The subject is instructed to inhale as strongly as possible, and the peak flow rate is then recorded. The test will be repeated three (3) times and the results averaged. For unilateral recording, one nostril is blocked with a tape, so that the subject can only inhale through the other nostril.
3. Research CT scans: The subject may receive a CT scan for non-clinical purposes with a cone beam office CT scanner (3D Accuitomo 170, J. Morita USA, Inc.) at the Department of Otolaryngology at The Ohio State University School of Medicine. This scan has a radiation dosage of roughly 12% that of a conventional head CT scan with a significantly lower associated health risk, while retaining excellent air-mucus contrast for CFD modeling. The recruitment strategy will reduce the need for research CTs and unnecessary radiation by recruiting patients who have been prescribed a sinus CT clinically, which will serve as the subject's baseline CT. Furthermore, if a post-treatment/surgery CT scan is clinically necessary for a patient after enrollment, it will be scheduled for the subject's second study visit. Through these measures, the need for research CT scans will be reduced to limit the number of research CT scans for all patients to one (1).
4. CFD Modeling: 3D numerical nasal models that are suitable for numerical simulation of nasal airflow and odorant transport will be constructed based on each subject/patient's CT scan and according to the method described by Zhao⁸. In brief, first the interface between the nasal mucosa and the air is delineated (using AMIRA[®]) on the CT scans. Then, the nasal cavity air space is filled with tetrahedral elements (ICEMCFD[®]). A finer mesh (prism layer) is created near the mucosal surface to more accurately model the rapidly changing near-wall air velocity and odorant concentration. Next, inspiratory and expiratory quasi-steady laminar nasal airflow^{8,9} is simulated (Fluent[®], Ansys Inc, USA) by applying a physiologically realistic pressure drop between the nostrils and the nasal pharynx. By varying the pressure drop and computing the changes in total airflow through the nose, the total nasal resistance can be determined, a numerical method of rhinomanometry. Through simulation, the following variables will be obtained: numerical nasal resistance, nasal mucosal cooling rate, and nasal airflow distribution patterns.
5. Adverse Event Evaluation – Subjects will be asked about possible side effects or adverse experiences related to the study procedure. All events will be documented on the proper Adverse Event Log and Adverse Event Case Report Form. Anticipated observations related to the study procedure will be tabulated, but will not be categorized as adverse events unless they require mitigation by the treating physician or are greater in severity, duration or degree of incidence than anticipated. Refer to Table 2 for a listing of anticipated observations as well as anticipated frequency, severity and duration.

7. Medications – Updates to current medications or any new or changed medications will be requested at each follow-up visit. The medication log will be updated to reflect any changes. In addition, any medications required as a result of intervention related to the study procedure will be documented and will correlate with the Adverse Event Case Report Form.
8. General Health Survey Subject will be asked to complete the SF-36 before and after treatment. The SF-36 is one of the most widely used generic measures of health-related quality of life and has been shown to discriminate between subjects with different chronic conditions and between subjects with different severity levels of the same disease. The SF-36 has also demonstrated sensitivity to significant treatment effects in a variety of patient populations.

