2.1 Primary outcome variables

The primary symptom outcome variables include self-reported Nasal Obstruction Symptoms Evaluation (NOSE) score and VAS of nasal obstruction.

The primary independent objective variables include several categories: 1) variables that index general disease severity (Computerized Tomography (CT) staging and endoscopic examination score), 2) peak inspiratory flow measurements of nasal physical resistance.

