4.0 PROCEDURES

4.1 Research Design

The study will be conducted by the Department of Otolaryngology, The Ohio State University School of Medicine, in conjunction with Aerin Medical. This study is a prospective, case series design, involving a group of patients with chronic nasal obstruction symptoms. The study is a longitudinal design, involving two test sessions: one at baseline (pre-treatment) and one at 90 days post-treatment.

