4.2 Study Size

Up to Twenty (20) patients meeting the inclusion/exclusion criteria will be recruited.

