For those potential candidates who agree to participate in the study by signing the IRB approved Informed Consent Form (ICF), a baseline evaluation will be conducted. Subjects will be considered enrolled once they arrive at the study clinic to undergo the procedure. At this time a subject identification number will be assigned along with the subject binder.

During the baseline and follow-up visits, the procedures listed below will occur

1. Endoscopic examination (video and pictures), Lund-Kennedy endoscopic scores
2. Peak nasal inspiratory flow
3. Cone beam CT scan (clinical CT at baseline; clinical or research CT at 90-day follow-up visit)
4. Nasal Obstruction Symptom Evaluation (NOSE) scale
5. Sino-Nasal Outcome Test (SNOT-22)
6. Visual analogue scale (VAS) rating severity of nasal obstruction
7. Computational modeling of nasal airflow based on CT scan of each visit.

During the baseline visit, data collection will be performed first, and then the Aerin Vivaer™ Treatment will be provided in the clinic by the physician. The styluses used in this study will be manufactured and supplied by the sponsor.

During the treatment, 0.5 ml of local anesthesia (lidocaine 1% with epinephrine 1:100,000) will be injected into the target tissue. The Vivaer stylus will be inserted into the nose and the electrode-containing tip will be positioned against the target tissue.

Subjects will have both nasal valves treated in a single study procedure session. Each nostril will be treated at up to 3 non-overlapping positions along the upper lateral nasal valve region.

Treatment settings to be used are:

Temperature.....60°C
Power 4 Watts
Treatment Time 18 secs
Cooling Time 12 secs

Accurate positioning will be confirmed by observing the temperature change on the RF generator screen as the stylus tip comes in contact with the target tissue.

No repeat ("touch-up") procedures will be permitted during the 90-day follow-up period.

Immediate Post-Procedure Care (prior to leaving the clinic)

At the discretion of the physician, the following care and instructions may be provided:

- Apply petroleum jelly to the treatment area as needed.

- The patient should be instructed not to manipulate the treatment site for 24 hours with the exception of any necessary hemostasis.

Study subjects will be reminded of their next follow-up visit and will be scheduled within the study window (90 ± 15 days).

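### Section 4.6 specifies no masking of the CT segmentation to visit or symptom scores; coding the scan files would be a cheap safeguard for the CFD variables

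*Combined protocol and SAP*

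**What the plan says.** Section 4.6, item 4 describes the CFD work in outline. For each scan, "the interface between the nasal mucosa and the air is delineated" in named software, the air space is meshed, and flow is simulated. The outputs are "numerical nasal resistance, nasal mucosal cooling rate, and nasal airflow distribution patterns". The item does not name the operator, the degree of automation, the reading order, any masking, or any repeatability check. It refers to a published method for the detail.

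The design is a single group: "This study is a prospective, case series design, involving a group of patients with chronic nasal obstruction symptoms", "involving two test sessions: one at baseline (pre-treatment) and one at 90 days post-treatment". Section 4.2 sets only a ceiling: "Up to Twenty (20) patients meeting the inclusion/exclusion criteria will be recruited". Section 4.7 calls for one CFD model per visit. It takes the baseline CT from clinical care and allows a clinical or a research CT at day 90.

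Section 2.1 says "The primary independent objective variables include several categories", and lists CT staging, endoscopy score and peak inspiratory flow. Section 4.7 also lists "Endoscopic examination (video and pictures), Lund-Kennedy endoscopic scores" at both visits.

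The hypothesis in section 4.9 is about airflow and cooling at the nasal valve, which are CFD outputs. That section plans Spearman correlation, multiple regression, linear discriminant analysis and logistic regression to relate the independent variables to symptoms, with a Holm-Bonferroni correction. Its repeated-measures ANOVA is confined to VAS, NOSE, SNOT-22 and peak inspiratory flow.

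Section 4.8, Internal Validity, deals only with recruitment and voluntary participation. Section 17.0 provides source data verification.

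**The concern.** Where the boundary is placed determines the computed airway. If placement leaves room for judgement, a small consistent difference between baseline and day-90 scans cannot be told apart from a real change in the valve, because there is no control group to show the same drift. The expected direction is known beforehand: section 3.0 says that healing should open the valve a little. Source data verification would not detect such a difference, since the value recorded is the value read.

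What is at stake is the explanatory part of the study: any CFD change that is reported, and the link between CFD variables and symptoms. There are two routes to bias. Knowing the visit can shift all day-90 readings together. Knowing the symptom scores can make the shift follow each patient's own improvement. They affect different analyses, so the remedy has to cover both.

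**Working it through.** **1. Search for a safeguard.** Sections 1.0, 2.0, 4.6 to 4.9, 16.0 and 17.0 contain no masking, mixed reading order, independent reading or agreement check for segmentation, CT staging or endoscopy. The plan gives no reader-error figure, so there is no figure of its own to reproduce. Everything below is illustration under stated assumptions.

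**2. Effect of boundary placement on resistance.** Assume laminar flow (as in the plan's model) through a narrow slit, so resistance R is proportional to 1/w³ for width w. Drawing the width a fraction d too large multiplies valve-segment resistance by 1/(1+d)³:

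- d = 2%: 1/1.02³ = 0.942, a fall of about 6%
- d = 5%: 1/1.05³ = 0.864, a fall of about 14%
- d = 10%: 1/1.10³ = 0.751, a fall of about 25%

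Section 4.6 computes total nasal resistance from nostrils to nasal pharynx. If the valve supplies a share s of the total, the fall in the total is s × [1 − 1/(1+d)³]. With s = 0.5 (assumption; the plan gives no share), the falls are about 2.9%, 6.8% and 12.4%.

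**3. A pre-post CFD comparison, if one is reported.** With two visits, a one-way repeated-measures ANOVA equals a paired t-test. Assume no true change, two-sided alpha 0.05, and a constant reading shift of b standard deviations of the change. The false-positive rate comes from the noncentral t distribution with n − 1 degrees of freedom and noncentrality b√n. For n = 20 and b = 0.3, the noncentrality is 0.3 × 4.472 = 1.34.

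| b | n = 20 | n = 15 |
|---|---|---|
| 0 | 5.0% | 5.0% |
| 0.2 | 13.6% | 11.2% |
| 0.3 | 24.7% | 19.2% |
| 0.5 | 56.5% | 43.8% |
| 0.8 | 92.4% | 82.1% |

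**4. The correlation screen.** Section 4.9 does not say whether correlations use pooled visits or changes, so both were simulated: 4,000 runs, n = 20, within-patient correlation 0.5 (assumption), and a CFD variable truly unrelated to symptoms. Symptoms fall by D SD and day-90 CFD readings shift by b SD on average. The table gives the percentage of Spearman tests with p < 0.05, before any Holm correction.

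| D | b | Pooled visits, uniform shift | Change v. change, uniform shift | Change v. change, shift follows own improvement |
|---|---|---|---|---|
| 1 | 0 | 6.2 | 5.1 | 5.1 |
| 1 | 0.3 | 7.5 | 4.7 | 19.8 |
| 1 | 0.5 | 11.1 | 5.2 | 45.9 |
| 1 | 0.8 | 20.1 | 5.6 | 81.6 |
| 2 | 0 | 3.7 | 5.3 | 5.3 |
| 2 | 0.3 | 8.6 | 5.4 | 9.3 |
| 2 | 0.5 | 18.1 | 5.0 | 15.7 |
| 2 | 0.8 | 40.8 | 5.5 | 34.0 |

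A uniform visit shift inflates pooled-visit correlations but leaves change-against-change correlations near 5%. Those become biased only if the shift tracks symptoms. The Holm correction addresses chance findings across many tests and does not remove a bias in the readings.

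**The case against.** **The documents are silent.** A reader might infer that staff do see the visit and the symptom scores. No section says so. The accurate statement is that masking is not specified.

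**Judgement in the segmentation is not established.** Item 4 is a summary that defers to a published method, and it describes the research scanner as giving good air-mucus contrast. A fixed automatic threshold would leave much less room for expectation. This stands as a limit on the size of the risk. It does not remove the point, because no such rule is stated.

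**The effectiveness result.** A reader might infer that the main finding is exposed. The ANOVA does not test CFD or endoscopy variables, and its four outcomes do not depend on segmentation. Predicting outcome from baseline models alone is also untouched by a shift at day 90.

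**Endoscopy.** A reader might infer that endoscopy carries the mechanistic answer. Section 2.1 makes it an index of disease severity; the hypothesis rests on CFD outputs. Masked rescoring is also less certain there. Endoscopy is part of routine care, Table 1 asks only for still photographs whereas section 4.7 lists video as well, and a clinician rescoring at most 20 known patients would be weakly masked. Endoscopy is therefore secondary here.

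**Masking may fail.** The CT source can differ between visits, and treated tissue may be recognisable. A scanner difference is also a systematic visit difference that masking cannot remove. Both stand, but symptom scores can be withheld in every case.

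**Conclusion.** The point holds as an omission that is cheap to repair. Section 4.6, item 4 specifies no masking for the step from which all CFD variables are computed, and nothing else in this uncontrolled two-visit design separates reading expectation from real change. The exposure is confined to reported CFD change, pooled-visit correlations and, if symptom scores are also known, change-against-change correlations, regression and classification.

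Its actual size is unknown. The 2% to 10% drawing shifts, the slit-flow rule, the valve's half share, the values of b and D, the within-patient correlation and the alpha are all assumptions. The falls of 6%, 14% and 25% apply to the valve segment only; it would be wrong to read them as falls in total nasal resistance. The plan gives no expected true change to set them against.

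**What to change.** Add to section 4.6, item 4:

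- Baseline and day-90 CT files receive random codes, with dates and visit labels removed.
- Whoever performs the segmentation works through them in mixed order with the same segmentation settings, without access to visit or to NOSE, VAS or SNOT-22 scores.
- The code is broken only after the models are locked.
- The segmentation rule is stated, including whether a fixed threshold is used.

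Apply the same coding to CT staging. Lund-Kennedy scoring from the stored images can optionally be handled in the same way where this needs no extra reader.

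The cost is file renaming, a code list and a short protocol statement, with no extra patients, visits, scans or reader. The downsides are that segmentation waits until both scans exist, and that masking to visit may be incomplete where the scan source or treated tissue gives it away. The change has to be made before segmentation begins, because analysis cannot remove the bias from readings made with knowledge of visit or scores.

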4.7 Study Phases

The study will be conducted in three phases as subjects are consented and evaluated for eligibility, treated and followed until study exit:

Phase 1 - Pre-Admission Evaluation/Patient Consent

Phase 2 – Baseline/Treatment

Phase 3 – Follow-Up 90 Days (+/- 15 days) Post-Procedure / Study Exit

The assessments to be performed during each phase are listed in Table 1.

Pre-Admission Evaluation/Patient Consent

Patients presenting with symptoms associated with nasal airway obstruction will be approached with the study and asked if they are willing to volunteer participation. Patients will initially be asked about duration of symptoms and conservative measures used for their condition. Any known concomitant nasal conditions and past nasal surgeries will be discussed to understand if they are potential candidates for the study.

Table 1. Schedule of Assessments

Assessments	Screening / Evaluation	Baseline/Study Procedure	Immediately Post-Treatment	90 day Follow-Up / Study Exit (+/- 15 days)
Informed Consent	X			
Demographics and Medical History	X			
Physical Exam and Vital Signs		X		
Medication Review		X		X
SF-36 Quality of Life Questionnaire		X		X
NOSE Score	X			X
Study Procedure		X		
Endoscopic Assessment of treatment area (with representative still photographs)		X	X	X
Cone beam CT scan (clinical or research)		X		X
Sino-Nasal Outcome Test (SNOT-22)		X		X
Peak Nasal Inspiratory Flow (PNIF)		X		X
Visual Analog Scale (VAS) of nasal obstruction		X		X
Adverse Event review			X	X
Pregnancy test (if female of child bearing potential)		X		

Informed Consent

Informed consent will be obtained as outlined in 21 CFR Part 50 and the Good Clinical Practice: Consolidated Guidance (ICH, April 1996).

A research study member at the approved study site will speak with the study candidate about the purpose of the study and investigational research. Explanation of the study background, study procedure, follow-up visit schedule, and study procedure risks and benefits will be

reviewed in detail with the patient. Patients will be given the time they need to read through the study information and informed consent document and to ask as many questions as necessary to make them comfortable with the study and the requirements. A patient willing to participate after undergoing the informed consent process will then be asked to sign the consent form and given a copy. The original will be kept on file.

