Adverse events (AEs) may occur during the treatment phase or during the follow-up phase. Adverse events occurring during the baseline assessment will be documented in the subject's medical record but will not count as related to the device or procedure. Each adverse event will be recorded and judged by the Investigator as to its relationship and level of relatedness to the device and/or procedure. In addition, the Investigator will identify the date of onset, severity and duration. All adverse events will be monitored until they are adequately resolved or explained.

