7.0 ADVERSE EVENTS

Adverse events (AEs) may occur during the treatment phase or during the follow-up phase. Adverse events occurring after the baseline assessment but before the treatment procedure will be documented in the subject's medical record but will not count as related to the investigational device or procedure.

Each adverse event will be recorded in the corresponding subject's CRF. The Investigator will make a judgement as to its relationship and level of relatedness to the study device and/or study procedure. In addition, the Investigator will identify the date of onset, severity and duration of the AE. All adverse events will be monitored until they are adequately resolved or explained. If a subject reaches the 90-day follow-up visit and is experiencing a new or ongoing adverse event, the study sponsor should be contacted to discuss the need and/or methods for continued surveillance of the event.

The Investigator must submit to the Sponsor a report of any Serious Adverse Event (SAE), Serious Adverse Device Effect (SADE) or Unanticipated Adverse Device Effect (UADE) within 24 hours of knowledge of the event.

Sponsor Contact: [name]
[contact]
[contact]
Email: [contact]

In addition, the Investigator will report adverse events to the reviewing IRB (*as applicable*) according to the local reporting requirements.

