25.0 DEFINITIONS AND ACRONYMS

Adverse Events

Adverse Event (AE) – any untoward medical occurrence in a subject (ISO 14155).

NOTE: This definition does not imply that there is a relationship between the adverse event and the device under investigation.

Serious Adverse Event (SAE) – an adverse event that (ISO 14155):

- led to a death,
- led to a serious deterioration in the health of the subject,
- resulted in a life-threatening illness or injury,
- resulted in a permanent impairment of a body structure or a body function,
- required hospitalization or prolongation of existing hospitalization,
- resulted in medical or surgical intervention to prevent permanent impairment to body structure or function,
- led to fetal distress, fetal death, a congenital abnormality, or birth defect.

Adverse Device Effect (ADE) – any untoward and unintended response to a medical device (ISO 14155)

NOTE: This includes any event resulting from insufficiencies or inadequacies in the instructions for use or the deployment of the device. This definition also includes any event that is a result of user error.

Serious Adverse Device Effect (SADE) – an adverse device effect that has resulted in any of the consequences characteristic of a serious adverse event or that might have led to any of these consequences if suitable action had not been taken or intervention had not been made or if circumstances had been less opportune (ISO 14155).

Anticipated Adverse Device Effect (AADE) – an adverse device effect which by its nature, incidence, severity or outcome has been previously identified in the previously identified in nature, severity, or degree of incidence in the investigational plan or application

Unanticipated Adverse Device Effect (UADE) – any serious adverse effect on health or safety or any life-threatening problem or death caused by, or associated with, a device, if that effect, problem, or death was not previously identified in nature, severity, or degree of incidence in the investigational plan or application (including a supplementary plan or application), or any other unanticipated serious problem associated with a device that relates to the rights, safety, or welfare of subjects (21 CFR 812.3.s and ISO 14155).

NOTE: The occurrence of a diagnostic or elective surgical procedure for a pre-existing condition, unless the condition becomes more severe or increases in frequency, would not be considered procedure or device-related.

Adverse Device Effect (ADE)

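### The adverse-event question is limited to procedure-related experiences, which is narrower than the protocol's own AE definition, so events that subjects do not attribute to the procedure may be under-ascertained

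*Combined protocol and SAP*

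**What the plan says.** - **The question.** Section 4.6, item 5: "Subjects will be asked about possible side effects or adverse experiences related to the study procedure". No other section words a question about adverse events.
- **The recording rule.** The next sentence of item 5 reads "All events will be documented on the proper Adverse Event Log and Adverse Event Case Report Form". Section 7.0 agrees: "Each adverse event will be recorded in the corresponding subject's CRF".
- **The definition.** Section 25.0 counts any untoward medical occurrence and adds a note: "This definition does not imply that there is a relationship between the adverse event and the device under investigation".
- **Who judges relatedness.** Section 7.0: "The Investigator will make a judgement as to its relationship and level of relatedness to the study device and/or study procedure". Section 4.7 says the same: "Each adverse event will be recorded and judged by the Investigator as to its relationship and level of relatedness to the device and/or procedure".
- **When.** Table 1 in section 4.7 has a row called "Adverse Event review", marked immediately after treatment and at the 90-day visit (± 15 days). The row has no relatedness limit and no question text.
- **Medications.** Section 4.6, item 7 asks about every new or changed medication, whatever the reason. It ties a medication to the AE form only where the medication was needed for an intervention connected with the study procedure.

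**The concern.** The definition and the two relatedness statements describe the usual order: collect every event, then let the investigator decide about cause. Item 5 reverses it for anything learned by asking. A subject who is asked only about procedure-related experiences has to settle cause before answering.

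This matters because some of the risks listed in section 8.1, such as infection, obstructive scarring and altered sensation, can appear late or resemble the nasal disease the subject already has. A subject could reasonably put them down to that disease. Events outside the nose are even less likely to be mentioned.

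Several parts of the protocol depend on complete ascertainment. Section 3.0 undertakes to record safety alongside efficacy. Section 8.3 has the sponsor watch for safety trends. Section 18.0 lists an unexpected incidence of known events among the reasons to discontinue. The 24-hour reporting requirement in section 7.0 runs from the investigator's knowledge of the event. The study has no control group, so a shortfall in reported events would not show up by comparison.

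**Working it through.** The protocol gives no figure on this point, so there is none to reproduce. The check sets the passages side by side.

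1. **Scope of the definition against scope of the question.** Section 25.0 covers all untoward occurrences, related or not. Item 5 of section 4.6 covers those related to the procedure. The second set lies inside the first. What is left over is the unrelated events, plus the related events that the subject does not recognise as such. The second group matters more for safety.

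2. **Who applies the filter.** Sections 4.7 and 7.0 name the investigator. Under item 5 the subject applies it first, by choosing what to mention.

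3. **Do the recording rules close the gap?** Items that are known must go on the log and CRF, with no relatedness condition. Those rules act on known events and do not find unknown ones.

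4. **Do other routes find them?**
   - *Medication review (item 7).* It can reveal an event that was treated with a drug. It misses events that led to no drug change. For a drug the subject thinks unconnected with the procedure, no stated step leads to an AE form.
   - *Endoscopy and CT.* After treatment, Table 1 has endoscopy of the treatment area immediately and at day 90, and CT at day 90. These can show lasting structural change. They can miss an event that has resolved, and they do not cover events outside the nose.
   - *NOSE, VAS, SNOT-22, SF-36 and peak flow.* These are scored outcomes. No section says that an answer or a change leads to an AE entry.
   - *Source records (sections 17.0 and 22.0).* Verification of safety data and retained medical records can bring events to light, but only those that reached a record the site holds.
   - *Safety follow-up (section 6.0).* It applies to certain withdrawn or lost subjects and carries no relatedness limit, but it supplies no question either.

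5. **Recall period.** After the immediate post-treatment check, Table 1 schedules one AE review. With the window it falls between 90 − 15 = 75 and 90 + 15 = 105 days after treatment, so one question has to cover 75 to 105 days.

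**Result.** The events at risk are those that the subject does not attribute to the procedure, does not volunteer, and that leave no trace by the routes in step 4.

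**The case against.** The strongest reply is that item 5 is a one-line summary and not an interview script. Its wording, which speaks of possible side effects, is softer than a demand for attributed events only. The CRF prompt is not in the documents and may be neutral. The same item goes on to require that all events be documented, and section 7.0 repeats this. The day-90 visit is full of examinations, and new medications are asked about whatever their cause. Obstructive scarring, for instance, lies in the area that endoscopy and CT examine.

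Much of this stands, and it limits the point. A reader might infer that unattributed events never reach the CRF, or that the investigator grades only what the subject has let through. The documents do not support either. Events that are volunteered, seen on examination or found through medications or records must be recorded and judged.

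Two further limits apply. The delay in learning of a serious event between visits comes largely from the visit schedule and would exist under any wording of the question. And section 4.9 plans no estimate of AE incidence, so no planned statistic can be called biased by a stated amount.

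What does not stand is the suggestion that the other routes make the wording harmless. A site looking for the question to ask will find only item 5, and step 4 of the check shows what the other routes miss.

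**Conclusion.** The inconsistency is real. The question is narrower than the definition in section 25.0, and it does not fit with the investigator making the relatedness judgement. The consequence is possible under-ascertainment of events that subjects do not attribute to the procedure and that no other assessment reveals. It is not a rule that keeps known events off the CRF.

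The direction, towards too few events, follows from the text. The size is unknown, because the documents give neither an event rate nor the proportion that subjects would fail to attribute. Any percentage would be invented.

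The conclusion assumes that sites ask the question as item 5 words it. If the CRF prompt is already neutral, what remains is a mismatch between protocol and form. The point should be corrected because safety is a stated purpose of the study and the change is small. It does not undermine the study as a whole.

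**What to change.** - Replace the question in section 4.6, item 5, and the matching CRF prompt, with an open one that does not mention cause. Ask it at each AE review in Table 1. For example: any new or worsened medical problem, doctor visit or hospital stay since the last contact.
- Add to item 7 that each new or changed medication is checked for an underlying adverse event, whatever its cause.
- Record every answer that meets the section 25.0 definition, keeping the existing rule for the anticipated observations in Table 2.
- Leave relatedness to the investigator, as sections 4.7 and 7.0 already provide.

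The cost is two short text changes, a revised CRF prompt, and a few unrelated events to record and grade among up to 20 subjects. No treatment or visit changes.
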